#### 14.4.2 ABRE Post-Approval Study Phase

The primary effectiveness endpoint of the post-approval study phase is Target Lesion Revascularization (TLR) through 36 months, defined as any re-intervention of the stented segment of the target lesion. Target limb revascularizations are adjudicated by the CEC to determine TLR status in addition to assessing relatedness and clinically driven status. Time-to-event analysis will be performed for the TLR rate through 36 months (1080 days), subjects with no TLR will be censored at the last contact date. Kaplan-Meier estimate and the 95% confidence interval for the freedom from TLR rate through 36 months will be reported.

#### 14.5 Study Success Criteria

The study success criteria set at the start of the study were as follows: the study will be considered a success if both the primary endpoints meet their respective performance goals. For the effectiveness endpoint this translates into observing a one-sided 97.5% lower confidence limit (LCL) of the point estimate above 75% and for the safety endpoint it means observing a one-sided 97.5% upper confidence limit (UCL) below 12.5%.

The ABRE post-approval study phase has no pre-specified hypothesis testing or study success criteria. All analyses will be presented with descriptive statistics.

#### 14.6 Handling of Dropouts and Missing Data

For those subjects not evaluable for primary effectiveness endpoint, multiple imputations will be carried out using the logistic regression approach for a dichotomous outcome using PROC MI in SAS for patients not experiencing the event and not having endpoint data for at least 330 days of follow-up.

The following variables will be included in the imputation model as covariates:

- Age
- Gender
- Race
- Ethnicity
- Diabetes
- Total occlusion
- Venous disease category
- Villalta score at baseline
- CEAP score at baseline
- VCSS class at baseline
- Reference vessel diameter
- Lesion length

If there are relatively few missing data points (e.g., <10%) for a given variable, a simple gender-specific imputation using the mean (for continuous variables) or median (for dichotomous or categorical variables) of the non-missing values will be done. If there are >10% missing data points, the variable will be excluded from the imputation analysis. Five data sets will be imputed from these covariates and will mimic different realizations of the missing data. For the endpoint, the numerator (the numerator is the point estimate of the treatment for the effectiveness endpoint) and its relevant standard error (the pooled standard error of

treatment for the effectiveness endpoint) will be pooled across the 5 data sets using established variance-adjustment methods (e.g., via PROC MIANALYZE in SAS) to create one overall numerator and denominator. The lower bound of the 97.5% pooled CI will be compared to the effectiveness PG.

The Tipping Point method will be adopted to further evaluate study primary objectives by assessing the impact of missing or unknown outcome data on study results. Tipping point analysis results for both primary effectiveness endpoint and primary safety endpoint will be reported.

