### 14.1 Performance Goals

#### 14.1.1 Performance Goal: Primary Effectiveness Endpoint

The primary effectiveness performance goal endpoint in the study is primary patency. The statistical hypothesis on this endpoint is that primary patency through 12 months will exceed a performance goal established from historical literature references using venous stenting as the treatment of choice. Formally, the null and alternative hypotheses to be tested appear below:

$$H_0: \pi \leq PG$$

$$H_A: \pi > PG$$

Where  $\pi$  is the primary patency at 12 months in the study population and PG is the performance goal, which is calculated as follows. An extensive and independent review of the available literature produced references on venous stenting in similar patient populations. These data are derived from published studies of venous stenting which measured target vessel patency as an endpoint. In order to estimate the expected rate of primary patency in the study population at 12 months, the review of the available literature was used (see Appendix A Scientific Literature Search).

Based on the literature, the weighted mean expected primary patency was 85.7%. By subtracting a margin of indifference of 10% from expected performance (85.7% - 10% = 75.7%); consequently, the value of 75% is therefore taken as the performance goal for the current study.

For analysis of the imaging component of primary patency, if a subject has both a valid venogram and DUS during the 12-month follow-up period then the venogram will be used. If no venogram is available, then the DUS will be used.

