## 14.2 Sample Size Calculation

**Primary Effectiveness:** Using the assumptions above on the performance goal and anticipated outcome, we assume desired power of at least 92% under difference testing relative to the performance goal at a one-sided alpha of 0.025. The resulting evaluable sample size required is then 160 subjects using exact binomial test for a single proportion. Accounting for attrition during follow-up, the sample size is augmented by 20% to 200 subjects. Every effort will be made, however, to minimize loss to follow-up.

**Primary Safety:** Using the assumptions above on the performance goal and anticipated outcome, we assume desired power of at least 92% under difference testing relative to the performance goal at a one-sided alpha of 0.025. The resulting evaluable sample size required is then 193 subjects using exact binomial test for a single proportion. Accounting for attrition during follow-up, the sample size is augmented by 3.5% to 200 subjects. Every effort will be made, however, to minimize loss to follow-up.

In summary, the overall power of the study is at least 84% while the effectiveness and safety performance goals are as follows:

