## 7.4 Handling of Missing, Unused, and Spurious Data and Dropouts

### 7.4.1 Multiple Imputation

For primary effectiveness endpoint, primary analysis will be performed using all evaluable data. Multiple imputation will be performed as sensitivity analysis to assess the robustness of the study data to the missing endpoints. For subjects not evaluable for primary effectiveness endpoint, the multiple imputation will be carried out using the logistic regression approach for a dichotomous outcome using PROC MI in SAS for subjects not experiencing the event and not having endpoint data for at least 330 days of follow up.

The following variables will be included in the multiple imputation model as covariates:

- Age
- Gender
- Race
- Ethnicity
- Diabetes
- Venous Disease category (aDVT vs. PTS vs. NIVL)
- Villalta score

- VCSS
- Reference Vessel Diameter
- Lesion length

If there are relatively few missing data points (<10%) for a given baseline variable, a simple gender-specific imputation using the mean (for continuous variables) or median (for dichotomous or categorical variables) of the non-missing values will be done. If there are >10% missing, the variable will be excluded from the imputation analysis. Five data sets will be imputed from these covariates and will mimic different realizations of the missing data. For the endpoint, the numerator (the numerator is the point estimate of the treatment for the effectiveness endpoint) and its relevant standard error (the pooled standard error of treatment for the effectiveness endpoint) will be pooled across the 5 data sets using established variance-adjustment methods (e.g., via PROC MIANALYZE in SAS) to create one overall numerator and denominator. The point estimate and the lower bound of the one-sided 97.5% pooled CI will be presented and compared to the primary analysis and the effectiveness PG

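### The patency imputation model fits 11 to 16 slopes to about 23 expected failures by ordinary logistic regression, so this sensitivity analysis can make a sound result look fragile

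*Protocol*

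**What the plan says.** Protocol 14.6 states that "multiple imputations will be carried out using the logistic regression approach for a dichotomous outcome using PROC MI in SAS" for subjects who have no event and lack endpoint data to day 330. It then says "The following variables will be included in the imputation model as covariates" and names twelve: age, gender, race, ethnicity, diabetes, total occlusion, venous disease category, Villalta, CEAP, VCSS, reference vessel diameter and lesion length. SAP 7.4.1 says "The following variables will be included in the multiple imputation model as covariates" and names ten, without total occlusion and CEAP.

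Both documents use five imputed data sets and compare the pooled one-sided 97.5% lower limit with the 75% goal. Both exclude a covariate only when more than 10% of its own values are missing. Neither gives the race coding, a limit on the number of parameters, or a rule for separated fits.

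SAP 7.4.1 makes the evaluable-subject analysis primary and imputation a sensitivity analysis. On sample size, protocol 14.2 says "The resulting evaluable sample size required is then 160 subjects using exact binomial test for a single proportion", and then "Accounting for attrition during follow-up, the sample size is augmented by 20% to 200 subjects".

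**The concern.** An ordinary logistic imputation draws its coefficients from a normal distribution around the maximum-likelihood fit. With few failures per slope that distribution is wide, and averaging over wide draws pulls predicted probabilities toward 50%. With true patency near 86%, that means downward. If a small category contains no failures, its coefficient separates, its variance becomes very large, and its members are imputed almost by coin toss.

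The purpose of this analysis is to show whether the patency result survives missing data. A model that pulls the rate down even when data are missing purely at random mixes its own over-fitting into that answer. A reader who sees the imputation limit fall below 75% would blame the missing data.

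**Working it through.** **Plan's own figure.** With n = 160 and success at 131 or more patent, P(X ≥ 131 | 0.75) = 0.0247 and P(X ≥ 131 | 0.857) = 0.9288. Both match SAP 6.3. The exact lower limit at 131/160 (81.9%) is 75.02%. Attrition: 160/(1 − 0.20) = 200, so up to 40 subjects to impute.

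**Expected failures.** 160 × (1 − 0.857) = 22.9.

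**Slopes.** Disease category takes two; each score is taken as one linear term.

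| List | Race coding | Slopes | Failures per slope |
|---|---|---|---|
| SAP | two groups | 11 | 2.08 |
| SAP | five groups | 14 | 1.63 |
| Protocol | two groups | 13 | 1.76 |
| Protocol | five groups | 16 | 1.43 |

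**Simulation inputs.**
- From the documents: category mix 26/30/44% for acute, non-thrombotic and post-thrombotic (SAP 6.4), with patency 84.0/94.8/80.5% (protocol Appendix A, Table XIII). Check: 0.26 × 84.0 + 0.30 × 94.8 + 0.44 × 80.5 = 85.7%.
- Assumed: race in two groups (15% in the smaller) or four to five groups with small cells, for example 86/8/3/2/1%; ethnicity 6–8%; diabetes 10–12%; total occlusion 30%; continuous covariates standard normal; 40 of 200 missing completely at random.

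**Method.** Fit by maximum likelihood on the 160, draw coefficients from N(b, V), impute by Bernoulli draws, M = 5. Pool by Rubin's rules: T = Ū + (1 + 1/M)B, limit = Q̄ − t(0.975, df)·√T, with df = (M − 1)(1 + Ū/[(1 + 1/M)B])².

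| Model | Bias in imputed subjects (points) | Primary passes, imputation fails (all trials) |
|---|---|---|
| 11 slopes, continuous or common binary covariates | −2.5 to −2.9 | 3.5–3.7% |
| SAP list, two race groups | −3.7 to −4.7 | 4.8–8.9% |
| SAP list, four race groups | −5.6 to −6.5 | 7.5–11.1% |
| Protocol list, two race groups | −4.1 to −5.1 | 5.9–9.6% |
| Protocol list, four to five race groups | −6.0 to −6.8 | 7.6–11.6% |

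In the last four rows, the smaller value assumes no covariate effect and the larger uses the documents' category effects. As a share of passing trials (divide by 0.9288), 3.5% becomes 3.8% and 11.6% becomes 12.5%. Other runs with category effects and the 86/8/3/2/1% race split reached about 14% of passing trials and 7.2 points.

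**Effect on the reported rate.** 40/200 × 2.5 = 0.5 points; 40/200 × 7 = 1.4 points.

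**What drives it.**
- *Missing fraction.* At 10% missing, disagreement is about 1–2%; at 5% it is 0.2–0.6%.
- *Separation.* In data sets where no coefficient separates, the bias is −2.5 to −3.3 points.
- *Number of imputations.* With no covariate effect, going from 5 to 100 imputations cuts disagreement from 4.8–7.6% to 1.6–3.9% of all trials, with bias unchanged. Even an intercept-only model disagrees in 1.3% with five imputations.

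**Remedies tried.**
- *Augmented likelihood on the SAP list.* Disagreement fell from 10–14% to 3–4% of passing trials. In two settings where covariates drove both missingness and failure, pooled bias moved from −0.8 to −0.5 and from −1.2 to −0.7 points.
- *Firth penalty on the full lists.* Disagreement fell from about 8–12% to 4–6% of all trials, but imputed patency stayed 4.3 to 5.8 points low. A penalty alone is therefore not a complete cure.
- *Disease category only.* Unpenalised, with category effects, it still disagreed in 6.5% (2.7% with 100 imputations). Augmented, it did well under purely random missingness (2–3% of passing trials). Where the dropped covariates drove both missingness and failure, it biased the rate upward: by 0.4 to 1.4 points in one set of runs and 0.9 to 2.0 in another.

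**The case against.** Much of the opposing case stands, and it limits the size of the point.

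- *Role.* SAP 7.4.1 makes imputation a sensitivity analysis, and the success criteria in protocol 14.5 do not use it. A reader might infer that the model could cost the trial its primary result; the documents do not support that.
- *Direction.* Under purely random missingness the error is conservative. It can make a good result look weaker but does not manufacture a pass.
- *Other checks.* Both documents plan tipping-point analyses and the SAP adds Kaplan-Meier estimates. Neither depends on this regression.
- *Inputs.* The race, ethnicity and diabetes frequencies are in neither document. The 20% is a planning allowance, not an observed loss. How the SAS procedure treats separated fits was not tested.
- *The two lists.* The SAP version history records a covariate update in version 3.0, so the mismatch is largely a protocol text that was not aligned.
- *Short lists.* A reader might infer that cutting to disease category alone solves the problem. The upward bias above shows that it can exchange a conservative error for one that favours passing.

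What survives is the over-fitting itself. It appeared under every list and coding tried, including the mildest, and an analysis meant to show robustness should not carry a bias of its own making.

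**Conclusion.** The point holds in a limited form. The failures-per-slope count (1.4 to 2.1) follows from the plan's figures and the race coding. At 20% missing completely at random, and under the assumed covariate frequencies, imputed patency is about 2.5 to 7 points too low, the pooled rate about 0.5 to 1.4 points too low, and the imputation limit contradicts a primary pass in roughly 4–14% of passing trials. At 10% missing that is about 1–2%.

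Two stronger readings should be avoided. The reported patency rate is not 5 to 7 points too low: that size applies only to the imputed subjects, and only in the upper part of the range. Nor is a disagreement in about one trial in nine a fixed property of the plan. It needs real category effects, the full 20% loss and, in several of the runs, sparse race cells as well; part of it comes from using five imputations.

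**What to change.** In protocol 14.6 and SAP 7.4.1:

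1. Fit the imputation model with a data-augmented or penalised logistic likelihood, and state how separation is handled.
2. Use one reconciled covariate list in both documents.
3. Drop or collapse sparse terms (race groups, ethnicity, diabetes) and state the coding. Keep disease category and the plausible predictors of both failure and missingness, for example lesion length and Villalta score.
4. Raise the number of imputations to about 50.

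The 12-month data were already collected and submitted when the current protocol was issued. This should therefore be a labelled supplementary run beside the planned one, reported with its justification as protocol section 14 requires for deviations from the analysis plan.

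The cost is a few lines of text, a changed imputation call and one rerun. The downside is that slightly fewer covariates support the missing-at-random assumption. The four changes were not simulated together, so their combined effect should be checked before the run is reported.

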## 14.7 Assessment of Data Pooling

Poolability of data across clinical study sites is justified on a clinical basis (i.e. all study sites use the same protocol). The sponsor monitors the site for protocol compliance, and the data gathering instruments are identical. The Food and Drug Administration also requires a statistical assessment of poolability. Poolability is assessed by comparing the baseline characteristics across study sites. For categorical baseline variables such as gender, a generalized Fisher's exact test or equivalent test will be used and for quantitative variables, parametric or non-parametric analysis of variance (general linear models or an equivalent procedure) will be used.

The above statistical analyses do not result in an impediment to pooling, but rather assess the balance of baseline covariates across study sites. If any baseline covariate is found to be statistically significant by this process, multivariate analyses will be done to determine if the imbalance affected study outcome. This is done by using both the variable found out of balance and study site as possible covariates.

It may be necessary to combine two or more low enrolling study sites into pseudo-sites to allow these analyses. Sites with fewer than 6 subjects will be ranked by enrollment from low to high. Starting from the lowest enrolling site, sites will be combined into a pseudo site until the combined size reaches the median enrollment among all sites. This process will be repeated until all resulting sites have enrollment equal to or greater than 6 subjects. This will be done in a manner to preserve the structure of the study and prevent bias.

Because the ABRE Study is being conducted in the US and outside the US (OUS), an analysis will be undertaken to determine if the study sites within the US and OUS subsets are homogeneous in the baseline covariates. Similar analyses will be conducted on gender. The statistical tests used will be the same as those discussed for site poolability.

Baseline characteristics to be considered as possible covariates are as following:

- Age
- Gender
- Race
- Ethnicity
- Coronary Artery Disease (CAD)
- Chronic Obstructive Pulmonary Disease (COPD)
- Myocardial Infarction (MI)
- Hyperlipidemia
- Cerebrovascular Accident (CVA)
- High Blood Pressure (HBP)
- Diabetes
- History of Tobacco Use
- History of Peripheral Artery Disease (PAD)
- Villalta score
- VCSS
- Venous disease category

If there are relatively few missing data points (e.g., <10%) for a given variable, a simple gender-specific imputation using the mean (for continuous variables) or median (for dichotomous or categorical variables) of the non-missing values will be done. If there are >10% missing data points, the variable will be excluded from the imputation analysis.

Poolability analysis will also be performed on the primary endpoints comparing across sites and geographical regions after adjusting for covariates difference. Logistic regression model will be utilized to include unbalanced covariates and site as an independent variable, and the study outcome as dependent variable to assess outcome difference. If the p-value of site effect is less than 0.10, further analyses will be undertaken to investigate the imbalance of the study outcome.

## 14.8 Minimizing Bias

Medtronic shall avoid improper influence on, or inducement of, the subject, monitor, any investigator(s) or other parties participating in, or contributing to, the clinical study.

Selection of subjects, treatment of subjects and evaluation of study data are potential sources of bias. Methods incorporated in the study design to minimize potential bias include (but are not limited to):

- For sites that are participating in other endovenous stent studies, which may have similar I/E criteria as the ABRE Study, a written process for avoiding selection bias is required.
- Subjects will be screened to confirm study eligibility with defined inclusion/exclusion criteria prior to inclusion. Sites are required to maintain a log of all subjects screened and enrolled for the study.
- Demographics (including race and ethnicity data) and medical history will be collected at baseline in order to later assess possible characteristics that may influence endpoints.
- Data collection requirements and study procedures will be standardized across all geographies.
- All geographies will follow the same version of the CIP and eCRFs.
- No more than 20% of expected inclusions may come from a single site.
- All study investigators will be required to meet the requirements of 21 CFR Part 54, Financial Disclosure by Clinical Investigators.

- All study site and Medtronic personnel will be trained using standardized training materials.
- Regular monitoring visits will be conducted to verify adherence to the CIP and source data.
- An independent CEC will be utilized to regularly review and adjudicate reported adverse events.
- An independent DSMB will be utilized to review data, help safeguard the interests of study subjects, and monitor the overall conduct of the study.
- Independent core laboratories will be utilized to interpret imaging results which will be used for the analysis.

## 15 Ethics

### 15.1 Statement(s) of Compliance

The ABRE Study is designed to reflect the good clinical practice (GCP) principles outlined in ISO 14155:2020. These include the protection of the rights, safety, and well-being of human subjects, controls to ensure the scientific conduct and credibility of the clinical investigation, and the definition of responsibilities of Medtronic and investigators.

The study will be conducted according to federal, national and local laws, regulations, standards, and requirements of the countries/geographies where the study is being conducted.

The study will also be conducted in accordance with the Declaration of Helsinki. The principles of the Declaration of Helsinki are implemented in this study by means of the patient informed consent (IC) process, Ethics Board approval, study training, clinical study registration, pre-clinical testing, risk benefit assessment, and publication policy.

In the US, the study will be conducted under an FDA Investigational Device Exemption (IDE) in compliance with 21 CFR Parts 11, 50, 54, 56, and 812 throughout the entire study (pivotal and post-approval study phases).

In addition, the study will be conducted in compliance with 21 CFR Part 11 and 54 in all participating geographies.

Outside US, the study will be conducted in compliance with ISO 14155:2020, MDD 93/42/EEC, and EU MDR 745/2017 as of Date of Application (where applicable) will also be followed. As described in section 12.2.4, reporting all adverse events is no longer required as of this CIP version which is a deviation from ISO 14155:2020 (7.4).

Where applicable, regulatory authority notification/approval will be done/obtained. Investigational sites will not be activated, nor begin enrolling subjects until the required approval/favorable opinion from the respective regulatory agency and Ethics Board has been obtained (as appropriate).

Additionally, any requirements imposed by a local regulatory agency or Ethics Board shall be followed, as appropriate.

Each site must provide Medtronic with a copy of the investigational site's Ethics Board approval letter and the Ethics Board-approved Informed Consent Form. Ethics Board approval letters must contain the following elements:

- Study Title and the Medtronic Protocol Number;
- Medtronic's Protocol Version (revision letter and/or date of issue);
- A list of the documents reviewed at the meeting covered by the approval letter;
- If applicable, the required interval for the site's continuing review by the Ethics Board; and
- Expiration date, if applicable and/or allowed by the site's system, of the current approval.

If applicable, approvals for the continuation of the study at each investigational site must be kept current in accordance with the Ethics Board's review schedule, but at a minimum, the study must be re-reviewed by the Ethics Board regularly based on local requirements. All site communications to and from the Ethics Board must be forwarded to Medtronic as they are sent/received.

Medtronic will be informed by the Ethics Board and/or the investigator in case any action is taken by an Ethics Board with respect to this investigation.

This study will be publicly registered on [www.clinicaltrials.gov](http://www.clinicaltrials.gov) prior to first enrollment in accordance with the 2007 Food and Drug Administration Amendments Act (FDAAA) and Declaration of Helsinki.

